## Overview

Rise for Health is a 3-arm RCT of 2 interventions that address changing sitting in overweight, postmenopausal women over a 3-month period, compared with an attention control condition. This study is one of the three projects within the National Institute on Aging Program Grant named *Sedentary Time and Aging Mortality and Physical Function* (STAR). The program grant proposes a paradigm shift away from energy expenditure as the primary mechanism for improving health outcomes to investigate potentially feasible behaviors such as brief sit-to-stand transitions that expend little energy but engage muscles, improve postural blood flow, and may impact physical functioning in older adults. The STAR program includes 3 projects and 2 cores for studying postmenopausal women at risk of chronic diseases. In addition to the RCT described here (project 2), STAR includes a 3-condition randomized crossover laboratory trial of strategies to interrupt sitting time (n=78; project 1) and a study that optimizes new computational techniques for objectively measuring sedentary behavior to apply to existing prospective hip-worn accelerometer data from the Objective Physical Activity and Cardiovascular Disease Health in Older Women (OPACH) cohort of the Women Health Initiative (N>6000, project 3). All projects are investigating the consequences of sitting and brief sit-to-stand transitions on the mechanisms of healthy aging, including glucose regulation and endothelial functioning. The STAR program will provide a comprehensive evidence base that can inform public health guidelines on sitting behaviors and healthy aging.

## Study Objectives

Rise for Health will examine 3-month changes in biomarkers of healthy aging and physical, emotional, and cognitive functioning across a 3-arm randomized trial: (1) healthy living attention control (Healthy Living), (2) reduce sitting time (Reduce Sitting), and (3) increase sit-to-stand transitions (Increase Transitions). The study aims to enroll 405 postmenopausal women into the 3-month trial. The primary aim is to compare changes in glucoregulatory biomarkers (fasting plasma insulin and glucose, HbA1c, and HOMA-IR) and blood pressure over 3 months for the 2 intervention arms compared with the attention control condition. We hypothesize that, compared with those allocated to the attention control arm, participants in the 2 intervention arms will have greater improvements in glycemic control and blood pressure. In addition, we will evaluate the dose-response effects of sitting behavior changes on glucoregulatory biomarkers and blood pressure. We hypothesize that greater improvements in the target behavior will be associated with greater improvements in glucoregulatory biomarkers and blood pressure. The secondary aims of the study are to examine the effects of the intervention on physical, emotional, and cognitive functioning. This project will also explore (1) the modifying effects of age on the relationship between the 3 conditions and primary and secondary outcomes, (2) the psychosocial and mediators and moderators of changes in sitting behaviors, and (3) the differences in outcomes between the 2 sitting interruption intervention arms. The purpose of this paper is to describe the study protocol of Rise for Health, a 3-arm randomized trial, to assess ways of interrupting sitting in postmenopausal women.

The institutional review board of the University California San Diego (UC San Diego) approved all study procedures, and all participants will provide written informed consent. Study recruitment, participant safety, and progress are reviewed semiannually by an external independent data safety monitoring board appointed by the National Institutes of Health (NIH).

## Participants

### Eligibility

To be eligible, participants must be female and meet the following inclusion criteria: (1) currently 55 years or older; (2) sit for more than 7 hours on a majority of device-measured days, as assessed by activPAL (as given in the *Screening Visit* section); (3) do 70 or fewer sit-to-stand transitions on a majority of device-measured days, as assessed by activPAL; (4) no health conditions that would inhibit standing; (5) able to read and write fluently in English; (6) postmenopausal, defined as no menstrual period in the last 12 months; (7) BMI $\geq$ 25 kg/m^2 and <45 kg/m^2; (8) able to walk, stand, and perform sit-to-stand transitions without a high risk of falling, determined by the Short Physical Performance Battery (SPPB); and (9) able to travel to study visits. Exclusion criteria include (1) the use of insulin, (2) uncontrolled diabetes defined as HbA1c>10%, (3) uncontrolled blood pressure defined as systolic blood pressure>180 or diastolic blood pressure>110, and (4) participation in another research study or program that would impact the outcomes of this study.

## **Recruitment and Screening**

The primary methods of recruitment are contacting UC San Diego patients identified through electronic health records and contacting women in San Diego through marketing lists. Women are mailed a letter and a flyer to explain the study. Prospective participants are informed that the study staff would contact them or they could call to opt out. Additional recruitment methods include advertisements on social media platforms, such as Facebook and Instagram, flyers and listserv postings, and ResearchMatch.

Trained recruiters describe the study activities and conduct phone eligibility screening with potential participants. After phone screening, eligible women are scheduled for an in-person screening visit at UC San Diego.

## **Screening Visit**

At the initial visit, study requirements are reviewed and signed informed consent is obtained. Next, participants complete a medical history questionnaire and self-report their current medication and supplement use to confirm they do not have a medical condition that would inhibit standing or sit-to-stand transitions and do not use insulin. Measurements of height, weight, and blood pressure are taken to screen for BMI and blood pressure. Hip and waist circumference measurements are also recorded. Participants perform SPPB to assess physical functioning and the ability to safely stand and perform sit-to-stand transitions. If all the preliminary screening criteria are met, participants complete a battery of cognitive tests and questionnaires on self-reported demographics and PA. Participants are given an activPAL, a thigh-worn accelerometer that objectively measures sitting time and number of sit-to-stand transitions, and an ActiGraph GT3X+ (ActiGraph, LLC) accelerometer, a waist-worn device that objectively measures minutes of PA. Participants are shown how to attach activPAL using waterproof Tegaderm dressing so that it does not have to be removed, and replacement waterproof dressing is provided. Participants are asked to wear these devices for 24 hours continuously, except they are asked to remove the ActiGraph GT3X+ accelerometer before bathing or swimming for the next 7 days.

## **Baseline Visit**

Participants return to the clinic after at least seven days of wearing the two devices. Data from activPAL are screened for sitting time (more than 7 hours on a majority of measured days) and sit-to-stand transitions (70 or fewer transitions per day on a majority of measured days) to confirm eligibility. Participants provide fasting blood samples via a finger prick to screen for HbA1c. Those who pass these final eligibility criteria then have a venous blood draw taken by a certified phlebotomist and complete additional questionnaires. Participants receive a total of US \$35 for completing baseline measures. After all baseline assessments are complete, the participants are then randomized.

Randomization is stratified by BMI (overweight vs obese) and employment status (full-time vs nonfull-time employment). A computerized randomization scheme was created using the STAR program grant Biostatistics Core, using a random number generator. A stratified permuted block design is used in this study. After randomization, the participants review the expectations and requirements of their study group assignment (details given in the *3-Month Intervention* section). Data collectors and the principal investigator are blinded to the study group assignment.

## **3-Month Final Visit**

Before their final visit, participants are mailed the accelerometer and activPAL and asked to wear both devices continuously for 7 days before the visit. At this visit, participants repeat the same measures collected at the screening and baseline visits, including blood draw, anthropometric measures, battery of cognitive tests, SPPB, and questionnaires. Participants receive up to US \$110 for completing the final measures.

## **3-Month Intervention (Rise for Health)**

### **Reduce Sitting and Increase Sit-to-Stand Transitions**

The primary goal of the respective intervention arms is to interrupt the current sitting patterns by targeting 2 specific behavior changes: reducing the amount of time spent sitting (Reduce Sitting) or by increasing the number of sit-to-stand (STS) transitions each day (Increase Transitions). Both interventions, Reduce Sitting and Increase Transitions, use habit formation, social cognitive theory, and motivational interviewing techniques to support behavior change.

### **Health Coaching Sessions for Reduce Sitting and Increase Transitions**

Participants in both intervention arms receive 5 in-person, individual coaching sessions (weeks 1, 2, 3, 4, and 8) and 2 individual phone coaching sessions (weeks 6 and 11) over the course of the 12-week program. Participants

are asked to wear activPAL on their thigh continuously for the first 4 weeks of the study and then again during weeks 7 and 8 to help with self-monitoring, goal setting, and personalized feedback.

During the first 60-minute in-person session, the health coach provides an overview of the intervention and gives participants a binder of printed educational materials and safety tips, printed action plan forms, and tracking logs. First, participants are asked to share their motivation to join the study. Next, they review reasons for sitting, dangers of prolonged sitting, and benefits of breaking up sitting. Tips for safely reducing sitting or increasing sit-to-stand transitions based on group assignments are reviewed. The health coach models the target behavior by having participants in the Reduce Sitting arm practice standing for up to 5 minutes in the middle of the session, and participants in the Increase Transitions arm perform 3 brief sit-to-stand transitions in a row, holding each for 5 seconds, twice during the session. Participants are then given a wrist-worn activity band that is programmed to prompt sitting breaks based on group assignment (refer to the *Toolbox* section). Participants are shown graphs from activPAL data, either of time spent sitting or sit-to-stand transitions, depending on the group assignment (Figures 1 and 2). The health coach and participants use the graphs to (1) review a typical day and identify times during the day when participants may be able to take sitting breaks or perform sit-to-stand transitions, (2) set behavior change goals for the next week, and (3) create a specific action plan. Participants complete an action plan by identifying the specific strategy, location, days of the week, time of day, and tailored goals for the participant (number of minutes to reduce sitting by or number of transitions to complete). Participants brainstorm potential obstacles to following the action plan and solutions for overcoming each obstacle. Using motivational interviewing techniques, confidence is assessed and supported using a 0 (very low confidence) to 10 (very high confidence) scale (*ruler*). To further support behavior change, participants are provided with several tools they can choose to use. As people vary in their preferences and needs, a toolbox approach allows participants to select tools they want to try (refer to the *Toolbox* section). At the end of the session, participants are given an activPAL to wear for the next 7 days and bring in the following week so that they can review their behavior with their health coach. If the participant provides consent, the health coach sessions are audio recorded for quality checks and training.

At each subsequent coaching session, the health coach starts by assessing the adverse events that may have occurred since the last session. Then the health coach and the participant model the respective behavior, gradually increasing the number of minutes of standing or number of transitions each week until week 4, when standing time may be up to 10 minutes and the number of transitions at the beginning of the session may be 5. The health coach reviews any key topics from the previous session before introducing the new behavior change topic (Figure S1 in Multimedia Appendix 1). When worn, the previous week's daily activPAL data are reviewed using daily graphs of data (Figures 1 and 2), as described above for week 1. Graphs of weekly data are shown to discuss progress toward the target behavior (Figures 3 and 4). At each session, the health coach supports the updating of personalized goals and action plans. There is a second break to model the target behavior before completing the action plan. Discussions on barriers and solutions and the confidence to meet the goal are addressed. Weeks 2, 3, 4, and 8 sessions are carried out in person and last approximately 60 minutes each. Weeks 6 and 11 sessions are carried out over the phone and last approximately 30 minutes each. Participants are given activPAL to wear in weeks 1, 2, 3, 4, 8, and 9.

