### **Healthy Living**

Participants in the healthy living attention control (Healthy Living) condition receive an equal number of contacts as those in the 2 intervention arms. The first session (week 1) is delivered in-person, whereas the remaining

sessions (weeks 2, 3, 4, 6, 8, and 11) are delivered over the phone. During the first session, the health coach provides an overview of the study group and gives the participant a folder that includes information, worksheets, and resources on various healthy aging topics that may be discussed throughout the study. A new healthy aging topic is discussed at each session, with sleep and aging as the first topic. For all future phone sessions (weeks 2, 3, 4, 6, 8, and 11), the participant chooses which healthy aging topic to discuss. Example topics include safe driving, stress reduction, and healthy bones (Figure S1 in Multimedia Appendix 1). At each session, the health coach first provides an introduction to the selected topic. The health coach then reviews the learning objectives for the session, provides additional information about the health topic, and prompts the participant to complete the topic's worksheet. Then, the health coach and participant set the goal of the participant's choice related to the topic for that session and develop a related action plan. Using motivational interviewing techniques, confidence is assessed and supported using a 0-10 ruler question. At the end of each session, the health coach summarizes the session and confirms the date and time of the next session. The initial in-person session lasts 60 minutes, and subsequent phone sessions last 30 minutes.

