Sedentary Behavior Interrupted:
A Randomized Trial of 3-Month Effects on
Biomarkers of Healthy Aging and Physical
Functioning in the Real World (P2)

NCT03473145

August 26, 2025

Statistical Plan

Baseline characteristics were compared across the 3 treatment arms using ANOVA for continuous variables and χ^2 or Fisher exact tests for categorical variables. Study-related adverse events were tabulated by group using a standard medical dictionary for regulatory activities body system categories.

The primary analysis comparing the sit less and sit-to-stand interventions with the healthy living controls used the intent-to-treat principle. Linear mixed models (LMMs) were applied, allowing for the inclusion of partially complete records, thereby reducing complete case analysis biases. The model included baseline and 3-month outcomes as dependent variable; time (baseline, 3-month), group (active, control), and the group*time interaction were fixed-effect independent (categorical) variables. A subject-specific (random) intercept was included to model individual heterogeneity in outcomes. A significant group*time interaction indicated that outcome changes differed between that intervention and the control arm; this difference of outcome changes between intervention and control arms represents the intervention effect.

To reduce the chance of false positives, we first fit the aforementioned LMMs for 2 primary composite outcomes: (1) glucoregulatory outcomes defined as the average of 4 Z scores of insulin, glucose, HbA1c, and HOMA2-IR; and (2) blood pressure composite defined as the average of 2 Z scores of systolic and diastolic blood pressure. The Z score for each participant for a specific marker and time point was derived by subtracting the sample baseline mean from the participant's marker value at that time point and dividing this difference by the sample baseline SD. This composite score analysis represents an omnibus test of intervention efficacy across multiple (correlated) outcomes: rejection of the null hypothesis would suggest that the intervention (compared with controls) effected changes across components of the composite score. After this composite score analysis, we compared group differences for each of the outcomes; we present intervention results for the individual markers.

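### Does asking about adverse events at intervention coaching sessions, with no such question described for controls, undermine the by-group safety table?

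*Protocol*

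**What the plan says.** The protocol's section on health coaching for Reduce Sitting and Increase Transitions sets out "5 in-person, individual coaching sessions (weeks 1, 2, 3, 4, and 8) and 2 individual phone coaching sessions (weeks 6 and 11"). It then says of the sessions after the first: "At each subsequent coaching session, the health coach starts by assessing the adverse events that may have occurred since the last session". Directly after that question, coach and participant practise the target behaviour together.

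The Healthy Living section gives controls the same number of contacts, one in person and six by phone. Of the calls it says: "For all future phone sessions (weeks 2, 3, 4, 6, 8, and 11), the participant chooses which healthy aging topic to discuss". It follows each session through the topic material, worksheet, goal, action plan and confidence rating, and closes with: "At the end of each session, the health coach summarizes the session and confirms the date and time of the next session". An adverse-event question is not among the steps.

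Three other places bear on the point. Under Screening Visit, "participants complete a medical history questionnaire and self-report their current medication and supplement use". Under 3-Month Final Visit, "participants repeat the same measures collected at the screening and baseline visits, including blood draw, anthropometric measures, battery of cognitive tests, SPPB, and questionnaires". Under Study Objectives, "Study recruitment, participant safety, and progress are reviewed semiannually by an external independent data safety monitoring board".

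The SAP has one sentence on safety: "Study-related adverse events were tabulated by group using a standard medical dictionary for regulatory activities body system categories".

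**The concern.** A by-group table of adverse events invites comparison across columns, and that comparison is fair only if events were sought with similar effort in each arm. Read literally, the protocol has coaches asking about events six times in each intervention arm and never in the control arm, although control calls fall in the same weeks. Solicited reporting usually finds more events than spontaneous reporting, so control events could be under-recorded. A reader might then be unable to separate a true excess in the intervention arms from a product of the questioning.

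The silence on the control side is noticeable because that section is otherwise detailed: it mentions the confidence ruler and the booking of the next call. No section describes an elicitation procedure common to all three arms. The final visit repeats questionnaires, but the protocol does not say that the medical history is among them or that it was used to record new events. Contact mode differs too, since most intervention follow-ups are in person and all control follow-ups are by phone. Restricting the table to study-related events is not a full answer, because an event must be known before its relatedness can be judged.

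**Working it through.** **Step 1: reproduce the session counts.** Inputs are the contact weeks in the two coaching sections.

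- Intervention arms: 5 in person (weeks 1, 2, 3, 4, 8) + 2 by phone (weeks 6, 11) = 7 sessions. Without week 1, 7 − 1 = 6 follow-ups, in weeks 2, 3, 4, 6, 8 and 11.
- Control arm: 1 in person (week 1) + 6 by phone (weeks 2, 3, 4, 6, 8, 11) = 7 contacts, which agrees with the protocol's statement that contacts are equal. Follow-ups: 6, in the same weeks.
- Described adverse-event inquiries: 6 of 6 in each intervention arm, 0 of 6 in control.
- Mode of follow-up: 4 of 6 in person (weeks 2, 3, 4, 8) in the intervention arms, 0 of 6 in control.

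These are counts of what is described for the standard schedule. They do not measure capture of events.

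**Step 2: can the size of a bias be derived?** If the true risk is the same in all arms, the apparent risk ratio equals capture in the intervention arms divided by capture in control. Neither figure is in the documents. With an assumed 90% capture when asked:

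| Assumed control capture | Apparent risk ratio |
|---|---|
| 90% | 0.9 / 0.9 = 1.0 |
| 60% | 0.9 / 0.6 = 1.5 |
| 30% | 0.9 / 0.3 = 3.0 |

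The range runs from no bias to a threefold distortion and depends wholly on the assumed capture. The premise of equal true risk is also implausible for study-related events when only two arms receive a physical intervention. The table shows the mechanism and gives no estimate for this trial.

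**Step 3: what could be missed in control?** The SAP table holds study-related events only.

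| Source of a possible study-related event | Intervention arms | Control arm |
|---|---|---|
| Prescribed standing or sit-to-stand practice, weeks 1 to 11 | yes | not described |
| Device wear during the coaching period | yes | not described |
| Self-set goals and action plans | yes | yes, on topics such as safe driving or stress reduction |
| Blood draw, physical tests and device wear around the assessment visits | yes | yes |

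Only the self-set goals give controls a described route to a study-related event between calls. The last row arises around visits that every arm attends. The number of control events lost for want of a prompt is therefore probably small, though not necessarily zero.

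**Step 4: is the table built from the coaches' question?** The question comes immediately before the in-session practice of standing or transitions. It can be read as a safety check before physical activity, which the control calls do not include. The text supports that reading without proving it. No sentence in either document links the SAP table to coach-elicited events.

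**Step 5: what depends on the table?** The SAP plans no test or model of adverse events between arms. The primary mixed models use the glucoregulatory and blood pressure composites, and adverse events enter none of the planned analyses.

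**The case for a change.** The strongest case for acting is that the remedy is nearly free: one sentence on how events were elicited in each arm, with a footnote if it differed. The count is right, the omission comes in an otherwise detailed section, and the programme is meant to inform public health guidelines, so a spurious excess of events in the intervention arms could mislead. Controls also set goals and undergo assessments, so study-related events can occur there.

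Much of this stands. The documents do not say how events were elicited in the control arm, and a reader of the table would benefit from knowing.

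The step to a table that cannot be compared across arms does not stand. It needs three things the documents do not show: that controls were not asked, that the table rests on the coaches' question, and that enough study-related control events arose between calls to matter. The monitoring board's review of participant safety and the SAP's by-group tabulation both suggest some recording in every arm, although neither says how it was done. A rule against drawing inference between arms would guard against an analysis that the SAP does not propose. Adding a question to the control calls is very probably too late, since the SAP is written in the past tense and dated August 26, 2025.

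**Conclusion.** No change to the plan follows. The difference in the descriptions is real: six inquiries per participant in each intervention arm and none in control, in the same weeks. It is a gap in a summary document and does not demonstrate unequal ascertainment. Its consequence is confined to one descriptive table of study-related events. The likely direction is to make the interventions look somewhat worse, so it would not conceal harm. Its size cannot be computed, but it is probably small given how little between-visit exposure the control arm has. No efficacy estimate, test or error rate is affected.

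This rests on three assumptions: that study-related control events between calls were few, that no formal comparison of adverse events is made beyond the tabulation, and that data collection is complete. What remains is a reporting detail. Analysts preparing the table can say how events were elicited in each arm and, if that differed, note it, without altering any planned analysis.
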